#### **8.3.2 Minimal Residual Disease**

Patients who are MRD negative at the end of the study will be summarized using frequency and percentage.

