## 1.0 Objectives

1.1 Primary: To assess the feasibility of blinatumomab post allogeneic hematopoietic cell transplantation (HCT) as consolidation therapy in patients with B-lineage acute lymphoblastic leukemia (ALL). Toxicities attributable to blinatumomab, acute GVHD, and secondary graft failure will be the parameters to define feasibility.

1.2 Secondary:

1.2.1 To evaluate the progression-free survival (PFS) rate at 1-year for patients with ALL compared to contemporary patient cohort.

1.2.2 To evaluate other efficacy endpoints such as overall survival (OS) and minimal residual disease (MRD) negativity rate in patients treated with blinatumomab for consolidation therapy.

1.2.3 To evaluate, non-relapse mortality (NRM) and chronic GVHD.

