#### 3.1.2 Blinatumomab dosage, administration, and schedule

Blinatumomab is administered as a continuous intravenous infusion (CIV). A single cycle of blinatumomab treatment is 4 weeks of CIV. Since patients are either in remission, or have minimal residual disease at time of treatment, the dosing schedule for minimal residual disease will be followed. Additionally, since both children and adults will be treated on this study, dosing will be weight- and BSA-based as per FDA guidelines for this drug. Please see section 5.3 for details of dosing administration.

The drug administration should not be interrupted, if possible. In case of infusion interruption, due to any technical or logistic reason, the interruption should be as short as possible and the infusion continued at the earliest time possible. Every interruption longer than 1 hour should be documented. If the interruption is longer than 4 hours, re-start of the infusion should be performed under healthcare supervision. The patient should be observed overnight for possible side effects after the restart in the hospital. Administration of dexamethasone premedication as described in Table 3 is recommended. If possible, the infusion duration before and after an interruption should total 28 days per treatment cycle.

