## 4.0 Patient Eligibility

### 4.1 Inclusion Criteria:

1. Patients 1-70 years of age.
2. Patients with B-lineage ALL in a) hematologic complete remission (CR) beyond CR1 at time of transplant; b) primary induction failure defined as requiring more than one line of induction therapy; c) positive minimal residual disease defined by positive flow >0.01% before or after transplant; or d) high risk cytogenetic or molecular features consisting of Ph-like phenotype, detection of BCR-ABL transcript by PCR with a sensitivity of 1/10,000, or detection of the t(9;22) translocation in any metaphases by cytogenetics at time of transplant, or presence of the MLL gene before or after transplant.
3. Received an allogeneic HCT within the last 100 days. Enrollment within 30-100 days after transplant, and after adequate recovery of counts defined as ANC  $\geq 0.5 \times 10^9/L$  without daily use of myeloid growth factor and platelet  $> 20 \times 10^9/L$  without platelet transfusion within 1 week, and adequate organ function to receive blinatumomab defined as creatinine clearance greater than 30 ml/min (or greater than 60 ml/min/1.73), ALT/AST  $< 5 \times$  ULN and serum bilirubin  $< 3 \times$  ULN.
4. Performance status of 0, 1, or 2. Karnofsky (or Lansky for subjects < 16 years old) performance status  $\geq 50$ .

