## 6.0 Study Evaluations

### 6.1 Pretreatment Evaluation

**Table 3. Pre-treatment evaluation schedule**

Procedure	Comments	Schedule
Informed Consent	Obtain standard informed consent approved by IRB	Within 14 days before therapy
Medical History	History of present illness, known allergies, prior cancer history as far as traceable including ALL regimens and drugs uses, and past medical/ surgical history as far as relevant.	Within 14 days of therapy
Physical Examination	Vital signs (temperature, heart rate, respiratory rate, blood pressure) and performance status.	Within 14 days of therapy
Concomitant Medications	Document concomitant medications, excluding prn and supportive care medications	Within 14 days of therapy
Hematology	CBC with differential and platelet count	Within 14 days of therapy
Biochemistry	at least creatinine, total bilirubin, uric acid, LDH, SGPT or SGOT, tacrolimus.	Within 14 days of therapy
Pregnancy test	Serum or urine, if female and /of child-bearing potential only	Within 14 days of therapy
Bone marrow	Aspirate and/or biopsy with flow cytometry for confirmation of diagnosis; cytogenetics	Within 30 days of therapy
Peripheral blood	Chimerism assessment	Within 30 days of therapy
Lumbar puncture	To assess for CNS disease, as clinically indicated	Within 30 days of therapy
Imaging studies	Chest X-ray and/or PET/CT as clinically indicated	Within 30 days of therapy

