## 6.2 Evaluation during study

**Table 4. Evaluation During Study**

Procedure	Comments	Schedule
Hematology	CBC with differential and platelet count	Weekly during each cycle
Biochemistry	at least creatinine, total bilirubin, SGPT or SGOT, tacrolimus	Weekly during each cycle
Physical Examination	Focused physical examination, including assessment for GVHD	Prior to each treatment cycle, and at study completion
Bone marrow	Aspirate and/or biopsy, MRD by multicolor flow cytometry, cytogenetics	Prior to each treatment cycle, and at study completion will be per the PI or treating physician discretion
Peripheral blood	Multiparameter FCI for immune reconstitution and PB chimerism	Prior to each treatment cycle, and at study completion will be per the PI or treating physician discretion
Optional Procedure: Peripheral blood	For banking in [name] laboratory at MDACC	Prior to each treatment cycle, at day 7 (+/- 2 days), day 14 (+/- 2 days) and at completion of each treatment cycle.

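### The single end-of-study MRD-negative percentage mixes clearance with maintained negativity, and an unstated denominator with a discretionary final marrow can move it either way

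*Combined protocol and SAP*

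**What the plan says.** Objective 1.2.2 lists among the efficacy endpoints the "minimal residual disease (MRD) negativity rate in patients treated with blinatumomab for consolidation therapy". The analysis in Section 8.3.2 is one sentence: "Patients who are MRD negative at the end of the study will be summarized using frequency and percentage". It gives no denominator, no split by MRD status at entry, no interval, and no rule for patients who relapse, die or have no final marrow. MRD stratification appears only in Section 8.3.1, for the contemporary cohort's outcomes.

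Patients can enter without detectable MRD:

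- Section 4.1 route (a) is "hematologic complete remission (CR) beyond CR1 at time of transplant". Like routes (b), induction failure, and (d), high-risk genetics, it does not require flow MRD.
- Route (c) is "positive minimal residual disease defined by positive flow >0.01% before or after transplant". A patient positive before transplant and negative at enrolment qualifies.
- Section 3.1.2 acknowledges the mix: "Since patients are either in remission, or have minimal residual disease at time of treatment".

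On measurement, Table 3 schedules a marrow within 30 days of therapy: "Aspirate and/or biopsy with flow cytometry for confirmation of diagnosis; cytogenetics". Table 4 gives the timing of the on-study marrow with MRD as "Prior to each treatment cycle, and at study completion will be per the PI or treating physician discretion". Section 7.1 ends the study at 1 year.

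**The concern.** A patient who is MRD negative at entry and stays so counts the same as a patient whose MRD cleared on treatment. The first result may reflect the transplant alone; the second is closer to evidence of drug activity. One percentage cannot separate them, and its value is set largely by how many patients start negative.

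The protocol's own supporting evidence is of the second kind. Section 2.3 cites conversion in 16 of 20 MRD-positive patients (80%), and 80% again in the 116-patient trial. A reader could set the trial's pooled percentage beside those figures although the two measure different things.

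The time point adds a second uncertainty. The endpoint is defined at study end, where the marrow is discretionary, and the plan does not say whether untested patients stay in the denominator.

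**Working it through.** The plan states no target, null rate or sample size for MRD, so there is no figure to reproduce.

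**Inputs**

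- Maximum sample size 30, read from Tables 5 and 6.
- f, the share MRD negative at entry: not given; assumed 0.5 to 0.9.
- s, the share of entry-negative patients still negative at study end without any drug effect: not given; assumed 0.70 to 0.95. The middle value 0.85 is suggested by Section 2.1, where 20 of 135 patients became MRD positive after transplant, so 115/135 = 85.2% did not. That was a general remission group, so it is only a guide here.
- c, the clearance rate among entry-positive patients: 0 for no effect, 0.80 for the conversion cited in Section 2.3.

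**Step 1: pooled rate with everyone tested**

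Pooled rate = f × s + (1 − f) × c.

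With c = 0, the lowest value is 0.5 × 0.70 = 35% and the highest is 0.9 × 0.95 = 85.5%. With s = 0.85:

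| f | c = 0 | c = 0.80 | Difference, points | Entry-positive, 30 × (1 − f) |
|---|---|---|---|---|
| 0.5 | 42.5% | 82.5% | 40 | 15 |
| 0.7 | 59.5% | 83.5% | 24 | 9 |
| 0.8 | 68.0% | 84.0% | 16 | 6 |
| 0.9 | 76.5% | 84.5% | 8 | 3 |

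The difference is (1 − f) × 80 points. Among entry-positive patients alone it is 80 points whatever f is, and the no-effect rate there is 0%.

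**Step 2: discretionary final marrow**

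Start from the no-effect rate p = 0.7 × 0.85 = 0.595. Let mN and mP be the testing probabilities of truly negative and not-negative patients. If only tested patients count, the rate is p × mN / [p × mN + (1 − p) × mP].

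- mN = 1, mP = 0.5: 0.595 / (0.595 + 0.2025) = 74.6%.
- mN = 1, mP = 0.25: 0.595 / (0.595 + 0.10125) = 85.5%.
- mN = 0.5, mP = 1: 0.2975 / (0.2975 + 0.405) = 42.3%.

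If half of all patients are tested regardless of status and an untested patient counts as not negative, the rate is 0.595 × 0.5 = 29.8%. The same underlying 59.5% can thus be reported well above or well below its value.

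**Step 3: precision after splitting**

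Exact 95% intervals for the entry-positive group: 12/15 gives 52–96%, 7/9 gives 40–97%, 5/6 gives 36–99.6%.

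**The case against.** The strongest reply is that the pooled rate matches the stated objective. Objective 1.2.2 asks for a negativity rate in treated patients, not a conversion rate, and the rationale in Section 5.3 is protection against relapse in the year after transplant. Staying negative is a relevant outcome for a high-risk patient who starts negative. That stands: maintained negativity is not an artefact. It is a reason to report it as its own quantity, not to merge it with clearance.

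A reader might go further and infer that the discretionary marrow inflates the rate. One scenario does so: 40% positive at entry, none clearing, every negative patient staying negative, and 30% of the cohort, all of them positive, untested and dropped, giving 0.60/0.70 = 86%. The documents do not support this as the expected direction. It needs a tested-only denominator that Section 8.3.2 does not state, and all losses falling among entry-positive patients. Section 2.1 reports that 41% of 32 patients with overt post-transplant relapse had no preceding MRD. Step 2 shows that the opposite bias is equally possible.

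Missing final marrows may also matter less than they seem. Cycle 4 falls at about 12 months after transplant (Section 5.3), so if only the completion marrow is discretionary, the marrow before cycle 4 lies close to study end for patients who get that far. Table 4 can, however, be read as making the pre-cycle marrows discretionary too.

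Finally, the consequence is limited. No test, threshold or decision rests on this summary, and PFS and OS capture relapse and death separately.

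**Conclusion.** The concern holds for interpretation of a secondary, descriptive efficacy endpoint. Followed as written, the plan yields a percentage that, under the assumed ranges, lies between 35% and 85.5% with no clearance at all. It separates no effect from 80% conversion by only 8 to 40 points (at s = 0.85), against 80 points among entry-positive patients. Pooling follows from the absence of any restriction, not from an explicit instruction.

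The discretionary marrow adds bias of unknown direction, not a demonstrated upward bias. The shares f and s and the testing probabilities are assumptions; the trial's actual mix is not in the documents. The feasibility conclusion, which rests on the stopping rules in Section 8.2, is unaffected.

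**What to change.** Replace the sentence in Section 8.3.2 with two summaries, using the pre-treatment marrow flow in Table 3 to set entry status:

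1. Conversion to MRD negative among treated patients MRD positive at entry.
2. Maintained negativity among treated patients MRD negative at entry.

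Give each as x/n with an exact 95% interval, with all treated patients of that group in the denominator. In both groups:

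- Relapse or death before study end counts as not negative and overrides any earlier negative marrow.
- In the main analysis, a patient with no study-completion marrow counts as not negative.
- One sensitivity analysis uses the last available pre-cycle marrow for patients alive without relapse; a second uses tested patients only.
- The number tested is reported for each group.

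Also clarify whether the discretion in Table 4 covers the pre-cycle marrows or only the one at study completion, because the first sensitivity analysis depends on them.

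The change is mainly to the analysis wording, since pre-treatment flow is already scheduled. The cost is precision: about 3 to 15 entry-positive patients of 30 under the assumed range, with intervals as wide as 36–99.6% for 5/6. The percentage is also likely to look less favourable, especially if many completion marrows are not done.

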#### **8.3.3 Non-relapse Mortality**

Non-relapse mortality (NRM) will be computed from date of allogeneic HCT to last known vital sign. The CI of NRM will be determined using the competing risks

method. The competing risk included will be relapse and patients who are still alive at the last follow-up date will be censored.

#### 8.3.4 Safety Measures

Safety will be assessed by vital signs, laboratory assessments, adverse events, and serious adverse events for all treated patients. Categorical measures will be summarized using frequencies and percentages while continuous variables will be summarized using mean, standard deviation, median, minimum, and maximum.

#### 8.3.5 Continuous Toxicity Monitoring

Continuous monitoring of toxicity will be assessed for all treated patients, beginning with the first cohort of five patients. Assuming a prior beta distribution of (0.6, 1.4), the study will terminate if the  $\Pr(\delta_t > 0.30 | \text{data}) > 0.85$ , where  $\delta_t$  is the toxicity rate attributable to the treatment. Toxicities are defined as any 1) grade 3-4 acute GVHD greater than 30%, 2) secondary graft failure >30%, or 3) NRM within one cycle of blinatumomab (i.e., 30 days). The decision rule for terminating for toxicity is presented in Table 5 and the operating characteristics for this rule are presented in Table 6. The method used to produce the decision rule and operating characteristics was designed by Thall, Simon, and Estey (1995).

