## 5.0 Treatment Plan

5.1 This is an open-label, single-arm, phase II clinical study.

5.2 All patients will be registered through Core. All of the enrolled subjects' concomitant medications will be collected and readily available in the MDACC electronic medical record and will not be entered into the CRF.

5.3 Patients will receive blinatumomab as continuous intravenous infusion over 4 weeks.

Since this study includes children and adults, dosing will be weight and BSA-based as per FDA approved dosing guidelines:

**For patients  $\geq 45$  kg**, the dose is 28 mcg/day administered as a continuous infusion on days 1-28 of each cycle.

**For patients  $< 45$  kg** the dose is 15 mcg/m^2/day (maximum 28 mcg/day) administered as a continuous infusion on days 1-28 of each cycle

All patients will receive 4 cycles of blinatumomab, with first cycle administered within the first 3 months following HCT, and then at 6 (+/- 2 weeks), 9 (+/- 2 weeks), and 12 (+/- 2 weeks) months following HCT (day of hematopoietic progenitor cell infusion). This schedule was selected to allow for treatment with blinatumomab during the one year following transplant when patients are at risk for relapse while the GVL effect is maturing and becoming robust.

5.4 GVHD prophylaxis will be as institutional standard.

5.5 CNS prophylaxis will be as institutional standard. However, craniospinal radiotherapy for prophylaxis post HCT is not permitted.

5.6 Tyrosine kinase inhibitor (TKI) use for patients with Ph+ ALL will be left to the investigator's discretion.

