**Table 6. Operating Characteristics**

True % of DLTs	Pr (stopping early)	Median Sample Size (interquartile)
0.10	0.01	30 (30, 30)
0.20	0.10	30 (30, 30)
0.30	0.36	30 (13, 30)
0.40	0.72	13 (5, 30)
0.50	0.94	5 (5, 13)

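### Section 8.3.5 sets no assessment window for acute GVHD or graft failure and no rule for pending outcomes; if pending patients count as event-free, Table 6 is only an upper bound on stopping

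*Combined protocol and SAP*

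**What the plan says.** Section 8.3.5 sets a Bayesian stopping rule on a single toxicity rate. The prior is given by "Assuming a prior beta distribution of (0.6, 1.4"), and the trial stops when the posterior probability that the rate exceeds 0.30 is above 0.85. On who is monitored it says: "Continuous monitoring of toxicity will be assessed for all treated patients, beginning with the first cohort of five patients". Table 5 lists the boundaries by total number of patients.

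The first two components are "grade 3-4 acute GVHD greater than 30%, 2) secondary graft failure >30"%. No time limit is attached to either. The third is "NRM within one cycle of blinatumomab (i.e., 30 days"), the only one with a window.

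Section 5.3 says "All patients will receive 4 cycles of blinatumomab", the first within 3 months of transplant and the others at about 6, 9 and 12 months. Table 4 schedules a "Focused physical examination, including assessment for GVHD" before each cycle and at study completion. Section 8.2 declares the primary objective met if the trial finishes without reaching a stopping rule.

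The documents do not say when a treated patient becomes countable, how a pending patient enters the calculation, whether accrual waits, how fast accrual is expected to be, or when GVHD or graft failure is expected to occur.

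**The concern.** A beta-binomial rule needs a yes or no for each patient in the denominator. With no window, a patient who has had one cycle and no event is neither: up to three more cycles, and any toxicity from them, may still follow. If such patients are entered as toxicity-free, the observed proportion is too low at each look and the posterior is pulled towards safety.

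Two things are at stake. The first is protection: more patients may be treated before the rule reacts to a rate above 30%. The second is the primary conclusion: feasibility is defined as not hitting this rule, so a rule that misses pending events also makes a declaration of feasibility more likely. Table 5 gives no toxicity count at n = 30 that would catch events arriving after the last patient enters.

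**Working it through.** **Inputs from the plan.** Prior Beta(0.6, 1.4); threshold 0.30; cut-off 0.85; first look at n = 5; maximum 30 (section 8.3.5, Table 5). I read the first two components as patient-level events, ignoring the percentages written into the definition.

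**Step 1: reproduce Table 5.** The boundary b(n) is the smallest x with 1 − F(0.30; 0.6 + x, 1.4 + n − x) > 0.85, where F is the beta distribution function. At n = 5, x = 2 gives 0.626 and x = 3 gives 0.875, so b(5) = 3. At n = 29, x = 11 gives 0.801 and x = 12 gives 0.890, so b(29) = 12. Every boundary from n = 5 to 29 matches.

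**Step 2: reproduce Table 6.** I used an exact binomial recursion with a look after each patient from n = 5 to 29 and every earlier outcome already known.

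| True rate | Table 6 | Recomputed |
|---|---|---|
| 0.10 | 0.01 | 0.010 |
| 0.20 | 0.10 | 0.097 |
| 0.30 | 0.36 | 0.358 |
| 0.40 | 0.72 | 0.718 |
| 0.50 | 0.94 | 0.938 |

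Table 6 is therefore the calculation with no outcome pending.

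**Step 3: direction of the error.** Let X(n) be the final number of toxicities among the first n patients and Y(n) the number seen so far. Y(n) ≤ X(n) always. If Y(n) reaches b(n), so does X(n), so the Table 6 calculation would have stopped at that n or sooner. If pending patients count as event-free, Table 6 is thus an upper bound on how often and how early the trial stops. This needs no simulation.

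**Step 4: size, under stated assumptions.** Accrual and onset are assumed. Entry is Poisson, onset is uniform from first dose over the window shown, and Table 5 is applied to all treated patients using events seen so far (up to 20,000 simulated trials per setting, accurate to about 0.01). The 9-month window is the span from a first cycle at month 3 to the last at month 12 (12 − 3 = 9).

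| Onset over | Patients/month | Stop early, true 0.40 | Stop early, true 0.50 | Not stopped, true 0.40 |
|---|---|---|---|---|
| Known at each look (Table 6) | any | 0.72 | 0.94 | 0.28 |
| 3 months | 0.5 | 0.68 | 0.92 | 0.32 |
| 3 months | 1 | 0.63 | 0.90 | 0.37 |
| 3 months | 2 | 0.53 | 0.85 | 0.47 |
| 9 months | 1 | 0.42 | 0.76 | 0.58 |
| 9 months | 2 | 0.15 | 0.40 | 0.85 |
| 9 months, one third of toxicities within 1 month | 1 | 0.51 | 0.83 | 0.49 |
| 9 months, one third of toxicities within 1 month | 2 | 0.30 | 0.62 | 0.70 |

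The last column is 1 minus the third. The last two rows allow for the 30-day mortality component; the one-third share is an assumption. With evenly spaced entry, onset within 1 month and at most 1 patient/month, Table 6 is unchanged.

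**Step 5: a final look.** Step 1's formula at n = 30 gives 0.764 for x = 11 and 0.863 for x = 12, so the rule's own criterion is 12 of 30. At a true rate of 0.40, P(X ≥ 12 | n = 30) = 0.57. A look after all follow-up is complete would thus hold a false declaration of feasibility to at most 1 − 0.57 = 0.43, whatever the delay, against 0.85 in the worst row above.

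**The case against.** A reader might infer that the plan counts each patient at first dose, that GVHD and graft failure appear months later, and that Table 6 is therefore wrong. The documents do not support that. The phrase about treated patients names a population and does not say when a patient becomes countable. No onset time is given anywhere. The rule counts only grade 3-4 acute GVHD; chronic GVHD is a separate secondary endpoint. With slow accrual or early onset the gap is small or nil.

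Three further objections stand in part:
- Mortality has a 30-day window, so delaying the whole toxicity rate exaggerates the worst case. The last two rows of the table allow for this.
- Detection is better than the pre-cycle examinations alone suggest. Table 4 adds an examination at study completion, section 9.1 collects adverse events with onset dates until 30 days after the last dose, and section 9.4 makes graft failure a serious adverse event.
- A true rate of 30% is the rule's own threshold, so stopping less often there is no failure, and the Table 6 median of 5 at a 50% rate is a knife-edge because P(at least 3 of 5) is exactly 0.50. Neither is used as evidence here.

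What remains is that the alternative reading, counting only patients with completed follow-up, also needs a window and a rule for pending outcomes. The plan states neither.

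**Conclusion.** The concern holds in conditional form. Section 8.3.5 leaves out the window for two of its three components and any rule for pending outcomes, and Table 6 is correct only if outcomes are known at each look. If pending patients count as event-free, the direction is certain: the trial stops less often and later than Table 6 says, and feasibility is declared too often.

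The size is not established, because it rests on assumed accrual and onset. At a true 40% rate the early-stopping probability ranges from no loss (onset within a month, at most 1 patient/month), through 0.68 to 0.53 (onset over 3 months, 0.5 to 2/month), to 0.42 and 0.15 (onset over 9 months, 1 and 2/month). Those last two become about 0.51 and 0.30 if one third of toxicities are early deaths. It would go too far to say that most or all of the 30 patients will be treated before the rule reacts; that follows only with slow onset and fast accrual. Because the rule is also the primary success criterion, the gap should be closed.

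**What to change.** 1. State in section 8.3.5 one assessment window per component, with its starting point.
2. State how pending patients enter the posterior. One option is to weight each event-free patient by the fraction of the window completed, using Beta(0.6 + events, 1.4 + sum of weights), which lets accrual continue. The other is to count only patients who have completed the window or had an event. If accrual waits for them, Table 6 is restored; if it continues, roughly accrual rate × window further patients will have been treated by the time of a stop (1 × 3 = 3, or 2 × 9 = 18).
3. Apply the rule once more when all patients have completed the window, before feasibility is declared, and add the n = 30 criterion to Table 5.
4. Recompute Table 6 at the expected accrual rate, or label it as assuming outcomes known at each look.

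GVHD and graft-failure onset dates can come from the existing examinations and adverse event collection; no new weekly GVHD assessment is needed.

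The cost is SAP text and a re-run of the operating characteristics. The stated stopping probabilities become less favourable by an amount that depends on accrual. At a true 40% rate, follow-up weighting gives about 0.64 (3 months, 2/month), 0.63 (9 months, 1/month) and 0.51 (9 months, 2/month) instead of 0.72, against 0.53, 0.42 and 0.15 with no rule for pending patients.

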**Table 2. Management of Toxicity and Blinatumomab Dosage Adjustments**

Toxicity	Grade	Action	
		Patient Weight	
		≥ 45 Kg	< 45 Kg
Cytokine Release Syndrome (CRS)	Grade 3	Withhold blinatumomab until resolved, then restart blinatumomab at 9 mcg/day. Escalate to 28 mcg/day after 7 days if the toxicity does not recur.	Withhold blinatumomab until resolved, then restart blinatumomab at 5 $\mu\text{g}/\text{m}^2/\text{day}$ . Escalate to 15 $\mu\text{g}/\text{m}^2/\text{day}$ after 7 days if the toxicity does not recur.
	Grade 4	Discontinue blinatumomab permanently	
Neurological Toxicity	Seizure	Discontinue blinatumomab permanently if more than one seizure occurs	
	Grade 3	Withhold blinatumomab until no more than Grade 1 (mild) and for at least 3 days, then restart blinatumomab at 9 mcg/day. Escalate to 28 mcg/day after 7 days if the toxicity does not recur. If the toxicity occurred at 9 mcg/day, or if the toxicity takes more than 7 days to resolve, discontinue blinatumomab permanently.	Withhold blinatumomab until no more than Grade 1 (mild) and for at least 3 days, then restart blinatumomab at 5 $\mu\text{g}/\text{m}^2/\text{day}$ . Escalate to 15 $\mu\text{g}/\text{m}^2/\text{day}$ after 7 days if the toxicity does not recur. If the toxicity occurred at 5 $\mu\text{g}/\text{m}^2/\text{day}$ , or if the toxicity takes more than 7 days to resolve, discontinue blinatumomab permanently.
	Grade 4	Discontinue blinatumomab permanently	
Other Clinically Relevant Adverse Reactions	Grade 3	Withhold blinatumomab until no more than Grade 1 (mild), then restart blinatumomab at 9 mcg/day. Escalate to 28 mcg/day after 7 days if the toxicity does not recur. If the toxicity takes more than 14 days to resolve, discontinue blinatumomab permanently.	Withhold blinatumomab until no more than Grade 1 (mild), then restart blinatumomab at 5 $\mu\text{g}/\text{m}^2/\text{day}$ . Escalate to 15 $\mu\text{g}/\text{m}^2/\text{day}$ after 7 days if the toxicity does not recur. If the toxicity takes more than 14 days to resolve, discontinue blinatumomab permanently
	Grade 4	Discontinue blinatumomab permanently	

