### **8.2 Primary Objectives**

The primary objective in this trial is feasibility. Treatment-related toxicities attributable to blinatumomab, an excess rate of acute GVHD, and an excess rate of secondary graft failures will be the parameters to determine feasibility. The successful completion of the trial without reaching stopping rules will indicate that the primary objective of the trial was met. Cumulative incidence time to GVHD will be computed from the date of allogeneic HCT to the date of event. The cumulative incidence (CI) of GVHD will be determined using the competing risks method. The competing risks included will be relapse and death, and patients who do not experience GVHD or relapse and are still alive at the last follow-up date will be censored at that date.

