**Table 5. Stopping Boundaries**

Total number of patients	Stop if this many patients have toxicity:
1-4	Never stop with this many patients
5	3-5
6-7	4-7
8-10	5-10
11-13	6-13
14-16	7-16
17-18	8-18
19-21	9-21
22-24	10-24
25-27	11-27
28-29	12-29
30	Always stop with this many patients

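### The stopping rule that decides feasibility monitors blinatumomab toxicity at most in its early fatal form, although Sections 1.1 and 8.2 make drug toxicity a feasibility parameter in its own right

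*Combined protocol and SAP*

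**What the plan says.** Section 1.1 sets the primary objective: "Toxicities attributable to blinatumomab, acute GVHD, and secondary graft failure will be the parameters to define feasibility". Section 8.2 repeats the three parameters, again with drug toxicity apart from GVHD and graft failure, and gives the success criterion: "The successful completion of the trial without reaching stopping rules will indicate that the primary objective of the trial was met".

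The only trial-level stopping rule is in Section 8.3.5. It has a Beta(0.6, 1.4) prior and stops when the posterior probability that the rate exceeds 0.30 is above 0.85, starting at five patients. The monitored quantity "is the toxicity rate attributable to the treatment", but the next sentence fixes the events: "Toxicities are defined as any 1) grade 3-4 acute GVHD greater than 30%, 2) secondary graft failure >30%, or 3) NRM within one cycle", with the cycle given as 30 days. Table 5 then counts patients: "Stop if this many patients have toxicity".

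Other drug toxicity is handled elsewhere. Section 3.3 and Table 2 manage it patient by patient; for grade 3 CRS, for example, "Withhold blinatumomab until resolved, then restart blinatumomab" at a stated dose. Section 7 removes individual patients from the study. Section 8.3.4 summarises: "Safety will be assessed by vital signs, laboratory assessments, adverse events, and serious adverse events for all treated patients". None of these sets a threshold for the trial as a whole.

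**The concern.** The primary conclusion is read off the stopping rule, so the rule should cover what the objective names. It covers acute GVHD (grades 3-4) and secondary graft failure directly. For the remaining parameter it offers only death without relapse within one cycle. The harms that Section 2.5 describes as particular to this drug (cytokine release, seizures, other neurological events) are missing from the count unless they are fatal within that window.

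The trial could therefore run to 30 patients, cross no boundary and be reported as feasible with respect to blinatumomab toxicity, when the rule monitored no non-fatal form of it. Describing the monitored rate as attributable to treatment makes that over-reading more likely.

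**Working it through.** **1. Does the rule reproduce?** Inputs from Section 8.3.5: prior Beta(0.6, 1.4), limit 0.30, cutoff 0.85, first look at 5 patients. The maximum of 30 is from Table 5. With r events in n patients the posterior is Beta(0.6 + r, 1.4 + n − r). The boundary is the smallest r with Pr(δ > 0.30) > 0.85. At n = 5, r = 2 gives 0.626 and r = 3 gives 0.8745, so the boundary is 3, as printed. Every Table 5 row from n = 5 to 29 reproduces.

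An exact recursion with a look after each patient from 5 to 29 gives:

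| True rate | Computed Pr(stop early) | Table 6 |
|---|---|---|
| 0.10 | 0.0103 | 0.01 |
| 0.20 | 0.0966 | 0.10 |
| 0.30 | 0.3576 | 0.36 |
| 0.40 | 0.7184 | 0.72 |
| 0.50 | 0.9384 | 0.94 |

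The sample-size medians and quartiles also match. Both tables are right for a single yes/no event per patient.

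**2. Objective against rule.**

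| Feasibility parameter (1.1, 8.2) | Counted in 8.3.5 as |
|---|---|
| Acute GVHD | Acute GVHD, grades 3-4 |
| Secondary graft failure | Secondary graft failure |
| Toxicity attributable to blinatumomab | At most, non-relapse death within one 30-day cycle |

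**3. What the rule sees.** Suppose, purely as an illustration, that all of the first five patients had non-fatal grade 4 neurotoxicity and none had a listed event. The rule records 0/5, and Pr(δ > 0.30) = 0.047. If those events counted, 5/5 would give 0.998 against the cutoff of 0.85. With no listed events the count stays at zero, and no Table 5 row stops at zero.

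**4. Effect of counting drug toxicity.** Let b be the rate of listed events and q the rate of added drug toxicity. The documents give neither b nor the overlap between the two. I assume b = 0.10 and b = 0.20 and bracket the overlap:

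- nested: max(b, q)
- independent: 1 − (1 − b)(1 − q)
- mutually exclusive: b + q

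For q the one documented rate used is grade 4 CRS, 1/70 = 0.0143 (Section 2.5). Grade 3 CRS is left out because Table 2 provides for restarting treatment after it. A 10% rate is added as an assumption only.

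| b (assumed) | q | Combined rate: nested / independent / exclusive | Pr(stop early) |
|---|---|---|---|
| 0.10 | 1/70 | 0.1000 / 0.1129 / 0.1143 | 0.0103 / 0.0150 / 0.0157 |
| 0.20 | 1/70 | 0.2000 / 0.2114 / 0.2143 | 0.0966 / 0.1163 / 0.1216 |
| 0.10 | 0.10 (assumed) | 0.1000 / 0.1900 / 0.2000 | 0.0103 / 0.0814 / 0.0966 |
| 0.20 | 0.10 (assumed) | 0.2000 / 0.2800 / 0.3000 | 0.0966 / 0.2904 / 0.3576 |

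At 1/70 the increase is at most 0.0157 − 0.0103 = 0.0054 (0.5 points) for b = 0.10, and 0.1216 − 0.0966 = 0.0250 (2.5 points) for b = 0.20. At the assumed 10% it is at most 0.0966 − 0.0103 = 0.0863 (about 9 points) and 0.3576 − 0.0966 = 0.2610 (about 26 points).

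**The case against.** The three listed events can be matched one to one with the three parameters, with early non-relapse death standing for drug toxicity. A reader might infer that drug toxicity goes wholly untested. The documents do not support that: it is monitored, but only in its early fatal form.

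A reader might also infer that non-fatal toxicity could never bear on the feasibility conclusion. That too goes further than the text. Section 8.2 asks for successful completion as well as for no boundary to be crossed, and Section 5.3 plans that "All patients will receive 4 cycles of blinatumomab, with first cycle administered within the first 3 months following HCT". If many patients stopped the drug for toxicity, one could dispute that the trial had been completed successfully. But the plan never defines success in this sense, so this gives no usable threshold.

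A rule built around GVHD, graft failure and early death is a coherent choice after transplant, with known drug toxicity managed per patient. That stands, and it is why the defect is a mismatch between objective and rule and not a wrong rule. The five-of-five case is extreme: Section 2.5 calls life-threatening neurological events uncommon. The 1/70 covers CRS only, in children with more than 25% marrow blasts (Section 2.4), whereas this trial excludes patients above 5% (Section 4.2).

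One might answer that the treatment-attributable label in 8.3.5, or the heading 'DLTs' in Table 6, already implies a wider event. The explicit list in 8.3.5 overrides the first, and the second is nowhere defined.

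**Conclusion.** The concern holds in this form: the objective names blinatumomab toxicity as a separate parameter, while the rule that decides the objective counts it at most as early non-relapse death. This needs correcting before the primary conclusion is drawn, because it determines what completion without stopping can be said to show. That judgement rests on the text of 1.1, 8.2 and 8.3.5 alone, and does not depend on the size of the shift in stopping probability.

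That shift is small at the only documented rate used: 0 to 0.5 points with listed events at 10%, and 0 to 2.5 points at 20%. Both base rates are assumptions, and the low and high ends are full and no overlap. Shifts of up to about 9 and 26 points need an assumed 10% drug-toxicity rate. The documents give no post-transplant rate, so they do not support a claim that the trial would probably miss serious toxicity. Nor is any figure in Tables 5 or 6 wrong.

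The percentages inside the event definition and the unlinked time frames are secondary and do not carry the rating.

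**What to change.** Reconcile Sections 1.1, 8.2 and 8.3.5 in one of two ways.

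- **(a) Narrow the claim.** Limit the feasibility conclusion in 1.1 and 8.2 to the events actually monitored, and say that non-fatal blinatumomab toxicity is reported descriptively. This is wording only; the price is a weaker claim.
- **(b) Widen the event.** The sponsor adds a blinatumomab-attributable toxicity item of its own choosing to the per-patient event, and states whether the 0.30 limit and the Beta(0.6, 1.4) prior still apply. If they do, Tables 5 and 6 stand. If not, both must be recomputed. This needs an amendment, an attribution decision per event and a justification of the limit and prior, and brings somewhat more early stopping, within the ranges shown above.

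In the same edit, remove the two 30% figures from the event definition, since a group rate cannot be part of a per-patient event, and use the event's name in Table 6. Also link the event to a stated time frame. The plan has three time references, none tied to Table 5: GVHD timed from HCT (8.2), study completion at 1 year (7.1) and 30 days after the last dose (9.1). A longer window delays the point at which a patient can be counted as event-free.

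Separately, Sections 3.3.1 and 7.3 use different attribution levels for grade 4 events, and the sponsor should reconcile them. The change above does not depend on that.
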